**Table 16-2 Follow Up Requirements for Liver Events and Laboratory Triggers**

Criteria	Actions required	Follow-up monitoring
Potential Hy's Law case a	
 
Discontinue the study treatment immediately
 
Hospitalize, if clinically appropriate
 
Establish causality
 
Record the AE and contributing factors (e.g., conmeds, med hx, lab) in the appropriate CRF
 
	ALT, AST, TBL, Alb, PT/INR, ALP and γGT until resolution c (frequency at Investigator discretion)
ALT or AST		
> 8 × ULN	
 
Discontinue the study treatment immediately
 
Hospitalize if clinically appropriate
 
Establish causality
 
Record the AE and contributing factors (e.g., conmeds, med hx, lab) in the appropriate CRF
 
	ALT, AST, TBL, Alb, PT/INR, ALP and γGT until resolution c (frequency at Investigator discretion)
> 3 × ULN and INR > 1.5	
 
Discontinue the study treatment immediately
 
Hospitalize, if clinically appropriate
 
Establish causality
 
Record the AE and contributing factors (e.g., conmeds, med hx, lab) in the appropriate CRF
 
	ALT, AST, TBL, Alb, PT/INR, ALP and γGT until resolution c (frequency at Investigator discretion)
> 5 to ≤ 8 × ULN	
 
Repeat LFT within 48 hours
 
If elevation persists, continue follow-up monitoring
 
If elevation persists for more than 2 weeks, discontinue the study drug
 
Establish causality
 
Record the AE and contributing factors (e.g., conmeds, med hx, lab) in the appropriate CRF
 
	ALT, AST, TBL, Alb, PT/INR, ALP and γGT until resolution c (frequency at Investigator discretion)

[figure not shown]
Criteria	Actions required	Follow-up monitoring
> 3 × ULN accompanied by symptoms b	
 
Discontinue the study treatment immediately
 
Hospitalize if clinically appropriate
 
Establish causality
 
Record the AE and contributing factors (e.g., conmeds, med hx, lab) in the appropriate CRF
 
	ALT, AST, TBL, Alb, PT/INR, ALP and γGT until resolution c (frequency at Investigator discretion)
> 3 to ≤ 5 × ULN (patient is asymptomatic)	
 
Repeat LFT within the next week
 
If elevation is confirmed, initiate close observation of the patient
 
	Investigator discretion Monitor LFT within 1 to 4 weeks
ALP (isolated)		
> 2 × ULN (in the absence of known bone pathology)	
 
Repeat LFT within 48 hours
 
If elevation persists, establish causality
 
Record the AE and contributing factors (e.g., conmeds, med hx, lab) in the appropriate CRF
 
	Investigator discretion Monitor LFT within 1 to 4 weeks or at next visit
TBL (isolated)		
> 2 × ULN (in the absence of known Gilbert syndrome)	
 
Repeat LFT within 48 hours
 
If elevation persists, discontinue the study drug immediately
 
Hospitalize if clinically appropriate
 
Establish causality
 
Record the AE and contributing factors (e.g., conmeds, med hx, lab) in the appropriate CRF
 
	ALT, AST, TBL, Alb, PT/INR, ALP and γGT until resolution c (frequency at Investigator discretion) Test for hemolysis (e.g., reticulocytes, haptoglobin, unconjugated [indirect] bilirubin)
> 1.5 to ≤ 2 × ULN (patient is asymptomatic)	
 
Repeat LFT within the next week
 
If elevation is confirmed, initiate close observation of the patient
 
	Investigator discretion Monitor LFT within 1 to 4 weeks or at next visit
Jaundice	
 
Discontinue the study treatment immediately
 
Hospitalize the patient
 
Establish causality
 
Record the AE and contributing factors (e.g., conmeds, med hx, lab) in the appropriate CRF
 
	ALT, AST, TBL, Alb, PT/INR, ALP and γGT until resolution c (frequency at Investigator discretion)
Any AE potentially indicative of a liver toxicity	
 
Consider study treatment interruption or discontinuation
 
Hospitalization if clinically appropriate
 
Establish causality
 
Record the AE and contributing factors (e.g., conmeds, med hx, lab) in the appropriate CRF
 
	Investigator discretion
a Elevated ALT/AST > 3 × ULN and TBL > 2 × ULN but without notable increase in ALP to > 2 × ULN b (General) malaise, fatigue, abdominal pain, nausea, or vomiting, or rash with eosinophilia c Resolution is defined as an outcome of one of the following: (1) return to baseline values, (2) stable values at three subsequent monitoring visits at least 2 weeks apart, (3) remain at elevated level after a maximum of 6 months, (4) liver transplantation, and (5) death.		

### 16.3 Appendix 3: Specific Renal Alert Criteria and Actions and Event Follow-up

**Table 16-3 Specific Renal Alert Criteria and Actions**

Serum Event	
Serum creatinine increase 25 – 49% compared to baseline	Confirm 25% increase after 24-48h Follow up within 2-5 days
Acute Kidney Injury: Serum creatinine increase ≥50% compared to baseline	Follow up within 24-48h if possible Consider study treatment interruption Consider patient hospitalization /specialized treatment
Urine Event	
Albumin-creatinine ratio (ACR) ≥1g/g or ≥100 mg/mmol; Protein-creatinine ratio (PCR ) ≥1g/g or ≥100 mg/mmol	Confirm value after 24-48h Perform urine microscopy Consider study treatment interruption / or discontinuation
For all renal events:	

Document contributing factors in the CRE: co-medication, other co-morbid conditions, and additional diagnostic procedures performed
 
Monitor patient regularly (frequency at investigator's discretion) until either:
 
Event resolution: sCr within 10% of baseline or protein-creatinine ratio within 50% of baseline, or
 
Event stabilization: sCr level with ±10% variability over last 6 months or protein-creatinine ratio stabilization at a new level with ±50% variability over last 6 months.
	

## 16.4 Appendix 4: Nasal Congestion Score Questionnaire

Figure 16-1 Nasal Congestion Score

1. Is your nose blocked?a

0 = Not at all      1 = Mild      2 = Moderate      3 = Severe

2. Is your sense of smell reduced?

0 = Not at all      1 = Mild      2 = Moderate      3 = Severe

[figure not shown]
3. Do you have a runny nose?

0 = Not at all      1 = Mild      2 = Moderate      3 = Severe

4. Do you feel dripping at the back of the nose?

0 = Not at all      1 = Mild      2 = Moderate      3 = Severe

a The Nasal Congestion Score (NCS) will be assessed with Question 1 only.

## 16.5 Appendix 5: SNOT-22 Questionnaire

[figure not shown]
Figure 16-2 SNOT-22 Questionnaire

I.D.: \_\_\_\_\_ **SINO-NASAL OUTCOME TEST (SNOT-22)** DATE: \_\_\_\_\_

Below you will find a list of symptoms and social/emotional consequences of your rhinosinusitis. We would like to know more about these problems and would appreciate your answering the following questions to the best of your ability. There are no right or wrong answers, and only you can provide us with this information. Please rate your problems as they have been over the past two weeks. Thank you for your participation. Do not hesitate to ask for assistance if necessary.

1. Considering how severe the problem is when you experience it and how often it happens, please rate each item below on how "bad" it is by circling the number that corresponds with how you feel using this scale: →	No Problem	Very Mild Problem	Mild or slight Problem	Moderate Problem	Severe Problem	Problem as bad as it can be	5 Most Important Items
1. Need to blow nose	0	1	2	3	4	5	
2. Nasal Blockage	0	1	2	3	4	5	
3. Sneezing	0	1	2	3	4	5	
4. Runny nose	0	1	2	3	4	5	
5. Cough	0	1	2	3	4	5	
6. Post-nasal discharge	0	1	2	3	4	5	
7. Thick nasal discharge	0	1	2	3	4	5	
8. Ear fullness	0	1	2	3	4	5	
9. Dizziness	0	1	2	3	4	5	
10. Ear pain	0	1	2	3	4	5	
11. Facial pain/pressure	0	1	2	3	4	5	
12. Decreased Sense of Smell/Taste	0	1	2	3	4	5	
13. Difficulty falling asleep	0	1	2	3	4	5	
14. Wake up at night	0	1	2	3	4	5	
15. Lack of a good night's sleep	0	1	2	3	4	5	
16. Wake up tired	0	1	2	3	4	5	
17. Fatigue	0	1	2	3	4	5	
18. Reduced productivity	0	1	2	3	4	5	
19. Reduced concentration	0	1	2	3	4	5	
20. Frustrated/restless/irritable	0	1	2	3	4	5	
21. Sad	0	1	2	3	4	5	
22. Embarrassed	0	1	2	3	4	5	

2. Please mark the most important items affecting your health (maximum of 5 items) \_\_\_\_\_ ↑

## 16.6 Appendix 6: ACQ-5 Questionnaire

Figure 16-3 Asthma Control Questionnaire - 5 - Page 1

---

---

# ASTHMA CONTROL QUESTIONNAIRE

(SYMPTOMS ONLY)

---

---

© 1997

QOL TECHNOLOGIES Ltd.

**Figure 16-4 Asthma Control Questionnaire - 5 - Page 2**

ASTHMA CONTROL QUESTIONNAIRE®

Page 1 of 1

Please answer questions 1 - 5

Circle the number of the response that best describes how you have been during the past week.

- |  |  |
|--|--|
| 1. On average, during the past week, how often were you woken by your asthma during the night?               | 0 Never
1 Hardly ever
2 A few times
3 Several times
4 Many times
5 A great many times
6 Unable to sleep because of asthma                          |
| 2. On average, during the past week, how bad were your asthma symptoms when you woke up in the morning?      | 0 No symptoms
1 Very mild symptoms
2 Mild symptoms
3 Moderate symptoms
4 Quite severe symptoms
5 Severe symptoms
6 Very severe symptoms            |
| 3. In general, during the past week, how limited were you in your activities because of your asthma?         | 0 Not limited at all
1 Very slightly limited
2 Slightly limited
3 Moderately limited
4 Very limited
5 Extremely limited
6 Totally limited          |
| 4. In general, during the past week, how much shortness of breath did you experience because of your asthma? | 0 None
1 A very little
2 A little
3 A moderate amount
4 Quite a lot
5 A great deal
6 A very great deal   |
| 5. In general, during the past week, how much of the time did you wheeze?                                    | 0 Not at all
1 Hardly any of the time
2 A little of the time
3 A moderate amount of the time
4 A lot of the time
5 Most of the time
6 All the time |

## 16.7 Appendix 7: Nasal Endoscopy

Nasal Endoscopy will be performed at the clinic using either a flexible fiber optic endoscope or a rigid endoscope. Polyps will be evaluated using the following scale:

Polyp Score	Polyp Size
0	No polyps
1	Small polyps in the middle meatus not reaching below the inferior border of the middle turbinate
2	Polyps reaching below the lower border of the middle turbinate
3	Large polyps reaching the lower border of the inferior turbinate or polyps medial to the middle turbinate
4	Large polyps causing complete obstruction of the inferior nasal cavity

Note: Scoring system is used to evaluate polyp size in each nasal passage by means of video nasal endoscopy. Nasal polyp score is the sum of unilateral polyp scores for each nasal passage. The scoring is modified to accommodate patients who have had a middle turbinectomy, such that the polyp must reach the top of the inferior turbinate to be graded as Score 2.

If the patient has polyps between the middle turbinate and septum meaning that polyps are coming from posterior ethmoid cells, one point was added, but not if the polyp scale was already confirmed. The grade of polyps in each nasal cavity of all patients will be taken into account in the results.

A video of each endoscopy will be recorded and initially saved locally within the clinical site. For endoscopy procedures performed at screening, the initial assessment of eligibility will be performed locally by the Investigator with the video files then uploaded for assessment of the NPS and confirmation of eligibility by central reading. This should be confirmed before the patient enters the run-in period. The endoscopy will be assessed at the end of the run-in with baseline NPS assigned locally by the Investigator. Should the Investigator deem the patient eligible for randomization then the baseline video will be uploaded for central reading assessment. The final result from the central readers **must** be received to re-confirm eligibility, prior to randomization. Upon confirmation of eligibility, the endoscopy assessments from Treatment Day 1 onwards, will also be uploaded to the vendors cloud based system for central reading assessment of the NPS. Should this upload not be possible due to local restrictions or logistics, the endoscopy video will be posted to the vendor on an encrypted USB drive. The vendor will utilize two independent experts who will each review the video and assign a score for NPS for that patient at the specific timepoint. Should there not be an agreement between the two reviewers, a third review will act as adjudicator and will make the final decision on the NPS.

Full training on the use of the vendors cloud based system will be provided.

The statistical analysis plan (SAP) describes all planned analyses for the Clinical Study Report (CSR) of study QAW039A2322, a phase IIIB, 16 week multicenter, randomized, double-blind, parallel-group, placebo-controlled study of fevipiprant once daily plus standard-of-care (SoC) for assessment of the efficacy in reduction of nasal polyp size in patients with nasal polyposis and concomitant asthma

The content of this SAP is based on the protocol of QAW039A2322 version v03.

The purpose of the statistical analysis plan is to describe the implementation of the statistical analysis planned in section 12 of the study protocol. Data will be analyzed by Novartis according to the data analysis section 12 of the protocol which is available in [Appendix 16.1.1 of the CSR](#). Important information is given in the following sections and the details will be provided, as applicable, in [Appendix 16.1.9 of the CSR](#).

[figure not shown]
1.1 Study design

This study uses a randomized, multicenter, double-blind, placebo-controlled, parallel-group study design to determine the ability of fevipiprant plus SoC compared to placebo plus SoC to reduce the size of Nasal Polyps in patients with asthma.

The study will include a Screening period of 2 weeks to assess eligibility followed by run-in period of 4 weeks where the patients will utilize Mometasone Furoate spray (200µg once daily administered as two 50µg actuations into each nostril) for baseline assessments treatment. The patients would then enter a treatment period of 16 weeks (with visits held every months for study procedures) and a follow-up period of 2 weeks following the last dose of study drug to collect additional data for safety variables.

The study will follow a 1:1:1 central randomization in each of the three arms (450 µg Fevipiprant+SoC , 150 µg Fevipiprant+SoC and Placebo)

The primary analysis will be performed after all patients have completed 16 weeks of study treatment or have discontinued early.

Approximately 93 patients will be enrolled into this study.

No formal interim analyses would be performed.

1.2 Study objectives and endpoints

Objective(s)	Endpoint(s)

Primary objective(s)
 
 To compare the reduction in nasal polyps score (NPS, assessed by Nasal Endoscopy with central reading) after 16 weeks of treatment with fevipiprant + SoC (150mg or 450mg once daily, separately) versus placebo + SoC in patients with nasal polyps with a NPS ≥ 4. 	
Endpoint(s) for primary objective(s)
 
 Reduction (in terms of change from baseline to week 16) in the Nasal Polyp Score, for fevipiprant (150mg or 450mg once daily, separately) as compared to placebo

Secondary objective(s)
 
 To evaluate the effect on symptoms as measured by the Nasal Congestion Score (NCS) with fevipiprant (150mg or 450mg once daily), compared with placebo. To evaluate the effect on Quality of Life as measured by the Sino-Nasal Outcome Test (SNOT 22) with fevipiprant (150mg or 450mg once daily), compared with placebo. To evaluate the effect on Smell as measured by the University of Pennsylvania Smell Identification Test (UPSIT) with fevipiprant (150mg or 450mg once daily), compared with placebo. 	
Endpoint(s) for secondary objective(s)
 
 Reduction (in terms of change from baseline to week 16) in NCS for fevipiprant (150mg or 450mg once daily, separately) as compared to placebo. Increase (in terms of change from baseline to week 16) in SNOT 22 for fevipiprant (150mg or 450mg once daily, separately) as compared to placebo. Increase (in terms of change from baseline to week 16) in UPSIT for fevipiprant (150mg or 450mg once daily, separately) as compared to placebo.

- To evaluate the general safety and tolerability of fevipiprant (150 mg and 450 mg, separately) as compared to placebo.
- Adverse events, ECG, vital signs and laboratory analysis following 16 weeks of treatment.

2 Statistical methods

This section contains information that will be used to draft CSR Section 9.7 on statistical analysis.

2.1 Data analysis general information

The final analysis will be performed by Novartis or a designated CRO. The most recent version of SAS and R software available in the statistical programming environment will be used for the analysis. There are no formal interim analysis to be performed.

2.1.1 Data included in the analysis

The analysis cut off date is defined as the date of last patient last visit during the 2 week follow-up period post the 16 weeks treatment period. The entire data collected up to the cut off date would be used under the scope of the analysis defined in the subsequent sections. All data with an assessment date or even start date (e.g. vital sign assessment date or start date of an adverse event) prior to or on the cut off date will be included in the analysis. Any data collected beyond the cut-off date will not be included in the analysis and will not be used for any derivations.

All events with start date before or on the cut-off date and end date after the cut-off date will be reported as 'continuing at the cut-off date'. The same rule will be applied to events starting before or on the cut-off date and not having documented end date. This approach applies, in particular, to adverse event and concomitant medication reports. For these events, the end date will not be imputed and therefore will not appear in the listings

2.1.2 General analysis conventions

Pooling of center: Unless specified otherwise, data from all study centers will be pooled for the analysis. Due to expected small size of centers, no center effect will be assessed.

Qualitative data (e.g., gender, race, etc.) will be summarized by means of contingency tables by treatment group; a missing category will be included as applicable. Percentages will be calculated using the number of patients in the relevant population or subgroup as the denominator.

Quantitative data (e.g., age, body weight, etc.) will be summarized by appropriate

descriptive statistics (i.e. mean, standard deviation, median, minimum, and maximum) by treatment group.

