2.2 Analysis sets

The **Screened Set (SCR)** will consist of all patients who provided informed consent

The **Full Analysis Set (FAS)** will be comprised of all randomized patients who meet both of the following criteria:

- Received at least one dose of study treatment
- Have a baseline NPS score ≥ 4 as measured by the central reader.

According to the intent to treat principle, subjects will be analyzed according to the treatment they have been assigned to at the randomization. However, if patients received study treatment without being randomized into the study they will be excluded from the FAS.

The **Safety Set (SAF)** includes all subjects who received at least one dose of study treatment. Subjects will be analyzed according to the study treatment received, where treatment received is defined as the randomized/assigned treatment if the patient took at least one dose of that treatment or if the patient received more than one treatment, then the patient would be analyzed according to the randomized treatment.

The analysis of the primary objectives will be performed on the FAS. The FAS will be used for the analysis of all other efficacy variables. The SAF will be used in the analysis of all safety variables.

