2.2.1 Subgroup of interest

No subgroups are defined in this study.

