2.3 Patient disposition, demographics and other baseline characteristics

2.3.1 Patient disposition

The following summaries will be provided overall and by treatment group: % based on the total number of FAS patients:

- Number of screened patients
- Number (%) of patients who were randomized
- Number (%) of patients who were randomized but not treated.
- Number (%) of patients who were treated
- Number (%) of patients who discontinued the study treatment phase

- Primary reason for study treatment phase discontinuation
- Number (%) of patients who have discontinued the study
- Reasons for discontinuation from the study.

Patient randomization numbers whether they completed or discontinued from the study will be listed, with date of last dose and primary reason for discontinuation, including the unblinding date if applicable.

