2.7.3 Handling of missing values/censoring/discontinuations

Despite all attempts to ensure complete follow-up for all patients, some patients may not be followed for nasal polyp size for the whole planned study duration of 16 weeks. The primary analysis will be done using a Mixed Model Repeated Measures (MMRM) approach. Under the assumption that the missing values are missing at random (MAR), this provides asymptotically unbiased and consistent estimates of the treatment effects.Safety analyses

2.7.4 To evaluate the general safety and tolerability of fevipiprant (150 mg and 450 mg, separately) as compared to placebo.

Safety and tolerability assessments would be based on the incidence of adverse events and serious adverse events, as well as vital signs, clinical laboratory evaluation, and 12-lead electrocardiogram findings.

For all safety analyses, the safety set will be used. All listings and tables will be presented by treatment group. Safety summaries will be primarily based on on-treatment data with selected tables also presented for all data after the first intake of study drug, while all databased safety data will be listed. The on-treatment period lasts from the date of first administration of study treatment to 1 day after the date of the last actual administration of any study treatment.

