2.7.7.2 Notable values

For selected laboratory parameters, abnormalities occurring at any time-point over the treatment period, considering all post-baseline data from scheduled, unscheduled and premature discontinuation visits will be summarized. Patients with any newly occurring or worsening on-treatment value meeting the clinically notable criteria will be counted under the applicable criteria.

For a patient to meet the criterion of a newly occurring clinically notable value, the patient needs to have a baseline value which is not clinically notable for that parameter. For a patient to meet the criterion of a worsening clinically notable value, the patient needs to have a baseline value which is not clinically notable and also have a worse post-baseline value. For patients with a missing baseline value, any post-baseline notable value will be considered as newly occurring.

The criteria for clinically notable values are presented in [Table 5.3.2](#).

Laboratory test units will be converted to standard units. Based on agreement within our standards, if we have a multi-region study the Blood Urea Nitrogen (BUN) / Urea test would be represented as BUN [mg/dL] for the regions used to conventional results (US, Latin America) and as Urea [mmol/L] for the regions used to SI (the international system of units) results. Therefore, both BUN and Urea parameters will be included in the data.

BUN is always reported as mg/dL and Urea as mmol/L. BUN and Urea are the same measurement in the lab and should be considered the same test. Hence, for the summary tables, it is expressed in SI units. Conversion to SI units includes the factor that incorporates a conversion from BUN to Urea as well as a conversion from mg/dL to mmol/L.

Listings of patients with notable laboratory values will be provided by laboratory parameter, treatment group, and patient number.

Additionally, box plot of change from baseline will be presented over time for ALT, AST, ALT/AST ratio, total bilirubin, creatinine, albumin,. ACR value will be considered missing if either the albumin or the creatinine values are missing. Similarly, PCR will be considered missing if either the protein or the creatinine values are missing.

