2.8 Other safety data

2.8.1 ECG and cardiac imaging data

ECG measurements include heart rate, QT interval, RR interval, PR interval, QRS duration, and Fridericia's QTc (calculated as $QTcF = QT / \sqrt[3]{RR}$ (in seconds), where $\sqrt[3]{}$ denotes the cube root).

ECG data measured more than 1 day after last intake of study drug are regarded as post treatment data and will not be summarized. All data will be included in the analyses regardless of rescue medication use.

Clinically relevant values

- The number and percentage of patients with newly occurring or worsening clinical relevant QTcF values (see [Table 2.8.1](#)) summarized at any time on treatment considering all post-baseline data from scheduled, unscheduled and premature discontinuation visits.

Table 2.8.1 Clinically relevant criteria for QTcF (Fridericia's formula)

ECG parameter (unit)	Clinically relevant range
Value considering newly occurring or worsening cases	
QTcF (msec)	≥ 450 (male)
QTcF (msec)	≥ 460 (female)
QTcF (msec)	> 500 (both)
Change from baseline	
QTcF	< 30
QTcF	30 – 60
QTcF	> 60

Clinically notable values

- A summary table will also be produced for number and percentage of subjects with notable QT and QTcF intervals (irrespective of the time point) using the following categories:
 - any treatment emergent (new) QTcF or QT interval ≥ 450 ms – 480 ms, > 480 ms – 500 ms or > 500 ms
 - QTcF or QT increase from baseline of ≥ 30 ms – < 60 ms, ≥ 60 ms
 - QTcF and QT increase from baseline of ≥ 30 ms plus QTcF interval ≥ 450 ms, > 480 ms or > 500 ms
 - QTcF increase from baseline of ≥ 60 ms plus QTcF interval ≥ 450 ms, > 480 ms or > 500 ms
- The number and percentage of subjects with noteworthy PR, QRS and HR interval changes will be reported using the below categories:
 - New PR > 200 ms to ≤ 220 ms; and > 220 ms
 - New QRS > 110 ms to ≤ 120 ms; and > 120 ms
 - PR increase $> 25\%$ to a value > 200 ms
 - QRS increase $> 25\%$ to a value > 120 ms
 - HR decrease $> 25\%$ to a HR < 50 bpm
 - HR increase $> 25\%$ to a HR > 100 bpm

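### The notable-value tables have no evaluable denominator, so patients without an on-treatment value stay in the base and percentages, chiefly for ECG, can be understated

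*SAP*

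**What the plan says.** SAP 2.1.2, in its convention for qualitative data, states: "Percentages will be calculated using the number of patients in the relevant population or subgroup as the denominator". Just before this it adds that "a missing category will be included as applicable".

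The population for safety is the safety set, meaning everyone who took at least one dose. SAP 2.2 says "The SAF will be used in the analysis of all safety variables", and SAP 2.7.4 repeats "For all safety analyses, the safety set will be used". SAP 2.2.1 says "No subgroups are defined in this study".

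The notable-value sections define the numerator only:

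- **Laboratory (SAP 2.7.7.2).** For a newly occurring value, "the patient needs to have a baseline value which is not clinically notable for that parameter". The definition of worsening in the same paragraph sets the same baseline condition. A patient with a missing baseline and a notable later value is counted as newly occurring.
- **ECG (SAP 2.8.1).** Tables give number and percentage of patients, and "ECG data measured more than 1 day after last intake of study drug are regarded as post treatment data and will not be summarized".
- **Vital signs (SAP 2.8.2).** The laboratory approach is carried over, with the same 1-day window.

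None of these sections names a denominator. Protocol Table 8-1 schedules post-dose ECG once (Week 16 or treatment discontinuation), hematology and chemistry at Weeks 8 and 16, and vital signs at Weeks 4, 8, 12 and 16.

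**The concern.** A patient can appear in the numerator of these tables only if a value was recorded inside the on-treatment window. With the whole safety-set arm as the base, a patient who has no such value is handled arithmetically like a patient who was measured and found normal.

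For ECG this can easily happen. A patient who stops early has one chance of a post-dose ECG, at the discontinuation visit. Protocol section 8 asks for that visit as soon as possible after premature discontinuation, and section 9.1.1 asks patients who stop treatment to return, where possible, for the scheduled assessments. Either visit may fall more than 1 day after the last dose, and that ECG is then not summarized.

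At stake is how the safety tables read. A percentage can be diluted, and if early stopping differed between arms it would be diluted unequally. A reader could not see this in the table, because no evaluable count is required.

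**Working it through.** **Inputs.** Arm size 31, total 93 and dropout 10% (Protocol 12.8.1, SAP section 3). The documents give no expected notable-value rate and no expected count of missing ECGs, so every event count and missing count below is assumed. All 31 randomized patients per arm are taken to be dosed.

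**Step 1: the plan's own figure.** With difference 1.5, SD 1.8, one-sided alpha 0.0125 and power 80%, the normal-approximation formula gives n = 2 × (1.8 × (z for 0.9875 + z for 0.80) / 1.5)² = 27.37 per arm. Then 27.37 / 0.9 = 30.4, rounded up to 31, and 3 × 31 = 93. The arm size reproduces and is used here only as N.

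**Step 2: the dilution.** With k cases, N treated and m evaluable, the table shows k/N, while the percentage among evaluable patients is k/m. The ratio of the two is m/N.

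**Step 3: planned dropout.** 10% of 31 is 3.1, so about 3. If all 3 lack an on-treatment ECG, m = 28 and m/N = 28/31 = 0.90.

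| Cases k | Shown, k/31 | Evaluable, k/28 |
|---|---|---|
| 1 | 3.2% | 3.6% |
| 2 | 6.5% | 7.1% |
| 3 | 9.7% | 10.7% |

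This is an upper bound on what dropout at that rate can do, because some who drop out will have an ECG within the window.

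**Step 4: range for 3 cases (shown as 9.7%).**

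| Not evaluable of 31 | m | k/m |
|---|---|---|
| 0 | 31 | 9.7% |
| 1 | 30 | 10.0% |
| 3 | 28 | 10.7% |
| 6 | 25 | 12.0% |

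**Step 5: unequal missingness, for illustration.** Assume 3 of 31 missing in one arm, 8 of 31 in another, and a true rate of 10% in both. The expected shown rates are 10% × 28/31 = 9.0% and 10% × 23/31 = 7.4%. The gap comes from missing ECGs alone. But 8/31 is 26%, more than 2.5 times the planned dropout, and nothing in the documents predicts it.

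**Step 6: patients notable at baseline.** Under SAP 2.7.7.2 they can be neither newly occurring nor worsening, since both definitions require a non-notable baseline. Eligibility removes most of them for QTcF and liver tests. Exclusion 5 uses the same 450/460 ms limits as SAP Table 2.8.1. Exclusion 34 removes ALT or AST above 2 × ULN at screening, against a notable limit of 3 × ULN. Some remain possible: women with QTcF of 450 to 459 ms in the category that starts at 450 ms regardless of sex, the new QT, PR and QRS categories, and glucose, hemoglobin and hematocrit.

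**The case against.** The strongest reply is that SAP 2.1.2 is a general default. It speaks of the relevant population or subgroup, which could be taken to mean evaluable patients, and it allows a missing category. Part of this stands: if the table shells already use evaluable patients, nothing is understated. SAP section 1 also defers detail to a CSR appendix that is not available here. But the SAP defines no evaluable subset and says there are no subgroups. A missing row tells the reader who was not measured; it does not change the base.

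Other points stand in full:

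- Beyond ECG the exposure is slight. Laboratory tests and vital signs have several post-dose visits, so only very early stoppers would have no value.
- The 10% is a dropout rate for the polyp-score comparison, not a rate of missing ECGs.
- The rule for a missing baseline works in the other direction, because it adds cases.
- The ECG and vital-sign tables give counts as well as percentages, discontinuations are shown by arm, all safety data are listed, and no test uses these percentages.
- Part of the ECG loss comes from a separate conflict: the on-treatment window is last dose plus 1 day in the SAP, but 30 days in Protocol 12.5.1. A denominator rule recovers none of the ECGs lost that way.

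An evaluable denominator also has its own assumption, that unmeasured patients resemble measured ones.

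**Conclusion.** The point holds as a minor gap in a stated rule. Read with the safety set as the population and no subgroups, SAP 2.1.2 leaves patients with no on-treatment value in the base of the notable-value tables, and percentages can be understated. At the planned dropout the effect is at most about 6.5% shown against 7.1% for 2 cases per arm, assuming every dropout lacks an on-treatment ECG.

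A reader might infer more, and the documents do not support it:

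- **That the SAP divides all counts by the full analysis set.** It does not. Safety uses the safety set. The full analysis set is the stated percentage base for disposition ("based on the total number of FAS patients"), not for these safety tables.
- **That the percentages are understated as a matter of fact.** This depends on how many patients turn out not to be evaluable; with none, the two percentages agree.
- **That the arm with more stoppers will look safer.** This needs missingness to differ by arm. The 3 versus 8 example is an assumption.
- **That baseline-notable patients materially dilute the QTcF and liver tables.** The exclusion criteria largely prevent that.

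**What to change.** In SAP 2.7.7.2, 2.8.1 and 2.8.2, with a cross-reference from 2.1.2:

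1. For each parameter, set the denominator to safety-set patients with at least one on-treatment value. Report n/m (%) and show the number not evaluable per arm.
2. For rows that count only newly occurring cases (the new QTcF/QT, PR and QRS categories), also require a baseline that is not notable or is missing, in line with how SAP 2.7.7.2 already treats a missing baseline.
3. For rows that combine newly occurring and worsening cases, first correct the definition of worsening in SAP 2.7.7.2. As written it requires a non-notable baseline, so it adds nothing to newly occurring. Then set the denominator to match. Excluding baseline-notable patients before this is settled could remove people whom the corrected definition is meant to count.

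The cost is SAP and table-shell wording, with no new data. The downside is that denominators vary by parameter, so tables carry an m for each row or parameter and their percentages no longer share one base.
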